## **C Study Objectives**

### **C1 Primary Aim**

The primary endpoint will be treatment failure at week 24:

Treatment failure will be defined as

- Before or at week 8 (any one of the following criteria)
  - new inflammatory lesions relative to baseline
  - anterior chamber cell or vitreous haze > 0.5+ on SUN scale
  - worsening of visual acuity by two or more rows on ETDRS (Early Treatment of Diabetic Retinopathy Study) chart
- After week 8 (any one of the following criteria)
  - new inflammatory lesions relative to baseline
  - 2-step increase in anterior chamber cell or vitreous haze
  - worsening of visual acuity by two or more rows on ETDRS chart

Grade '0' will denote zero cells present per high power field or no vitreous haze and a change of full number grade will represent a "step change" (e.g. a change from grade 1 to 0 is considered a 1-step change).

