### **D2 Clinical Data to Date**

We successfully treated one patient with off-label use of tofacitinib for refractory uveitis ([name] *et al. in submission*). Tofacitinib is also clinically efficacious and FDA-approved for the associated systemic rheumatologic diseases, rheumatoid arthritis and psoriatic arthritis, which are associated with inflammatory eye disease (8-10). Treatment with tofacitinib leads to a clinical response starting at 4-8 weeks after initiation of therapy (8-10). Administration of tofacitinib is approved for 5mg twice daily or 11mg extended release for rheumatoid arthritis. This dose has been in clinical practice since its FDA approval in 2012 with 19,406 patient-years of accumulated safety data.

---

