## **2.e Risks and Benefits**

As with other immunosuppressive treatments to control autoimmune diseases, the patients will be at increased risk of infection (20%). Other risks include nasopharyngitis (3% to 14%), hypertension (2%), headache (4% to 9%), rash (6%), acne vulgaris ( $\geq 2\%$ ), increased serum cholesterol (5% to 9%), diarrhea (4% to 5%), gastroenteritis (4%), nausea (4%), urinary tract infection (2%), anemia (4%), herpes zoster infection (5%; including disseminated cutaneous, meningoencephalitis, ophthalmologic), increased creatine phosphokinase (3% to 7%), increased serum creatinine ( $< 2\%$ ), upper respiratory tract infection (4% to 6%), and fever ( $\geq 2\%$ ).

Lymphoma and other malignancies have been reported in patients receiving tofacitinib

Tuberculosis (pulmonary or extrapulmonary) has been reported in patients receiving tofacitinib. Standard laboratory screening is performed in all patients to assess for latent / chronic infection, such as TB.

There is a risk associated with lack of efficacy. In the case of a treatment failure based on the primary outcome criteria, tofacitinib will be discontinued and the patient will be switched to an alternative steroid-sparing therapy at the discretion of the patient's treating physician.

Potential benefits include improved control of the ocular inflammatory disease, reduced corticosteroid usage, reduced intraocular pressure, improved visual acuity, and prevention of permanent vision loss. The participants may also derive benefit from contributing to medical research.

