## **2.i Cessation of tofacitinib therapy**

### **i Indications for cessation of tofacitinib therapy**

- Laboratory abnormalities:
  - New elevation of ALT or AST > 3x upper limit of normal
  - New leukopenia with ANC < 1.5
  - New anemia with hemoglobin <7 g/dl or a decrease of > 3g/dl
  - New renal failure that would preclude the safe administration of tofacitinib
    - Patients may restart tofacitinib after recovery of renal function
- Clinical events:
  - Shingles or opportunistic infection:
    - Patients that develop an opportunistic infection or shingles may opt to (1) withdraw from the study or (2) hold tofacitinib while undergoing treatment with antivirals or antibiotics
  - Hospitalization due to tofacitinib
    - Any patient hospitalized secondary to treatment with tofacitinib as determined by a rheumatology research clinician.
  - Infection with tuberculosis:
    - Patients that develop active mycobacterium tuberculosis. All patients will have undergone screening with a PPD or interferon gamma release assay to rule out TB at the beginning of the study.
  - Treatment failure after week 8

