### **ii Monitoring after tofacitinib cessation**

- If a patient is not a treatment failure as defined by the primary outcome measure at the time of tofacitinib cessation, they will be monitored for disease relapse
- If a patient is a treatment failure at the time of tofacitinib cessation, they will be switched to another steroid sparing agent at the discretion of their treating physician
- Patients who discontinue tofacitinib treatment will remain in the study and be followed to obtain safety data.

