### **3.f Prior and Concomitant Therapy**

All patients will be prescribed steroids with a uniform and pre-determined taper starting at prednisone 60mg daily (or equivalent) and tapering over 14 weeks to off.

Patients intolerant to an initial steroid-sparing therapy (e.g. methotrexate, azathioprine, or mycophenolate) will be started on tofacitinib and their prior steroid-sparing therapy will be discontinued. No other steroid sparing therapy will be initiated during the study period to avoid confounding of clinical efficacy.

Patients tolerant to prior steroid sparing therapy but with an incomplete control of their disease will have tofacitinib added to their steroid-sparing therapy. No other steroid sparing therapy will be initiated during the study period to avoid confounding of clinical efficacy.

Concomitant therapy with biologic steroid-sparing therapy such as adalimumab is prohibited due to the risk of infection.

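### The plan does not settle whether tofacitinib stops after a treatment failure at or before week 8: section 2.e stops it, while the cessation list in 2.i implies that it need not stop

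*Combined protocol and SAP*

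**What the plan says.** Section C1 (Primary Aim) sets two blocks of failure criteria. The first opens "Before or at week 8 (any one of the following criteria" and includes "anterior chamber cell or vitreous haze > 0.5+ on SUN scale". The second applies after week 8 and replaces that threshold with "2-step increase in anterior chamber cell or vitreous haze". New lesions and a two-row acuity loss appear in both blocks.

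Three places then deal with treatment after failure:

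- Section 2.e (Risks and Benefits): "In the case of a treatment failure based on the primary outcome criteria, tofacitinib will be discontinued", with a switch to an alternative agent. There is no time limit.
- Section 2.i, part i (the list of indications for cessation): the only efficacy entry is "Treatment failure after week 8".
- Section 2.i, part ii (monitoring after cessation): of patients who are failures when drug stops, "they will be switched to another steroid sparing agent at the discretion of their treating physician". Patients who stop drug stay in the study for safety follow-up.

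Section 3.f, on prior and concomitant therapy, adds "No other steroid sparing therapy will be initiated during the study period to avoid confounding of clinical efficacy". It states this for patients intolerant of an earlier agent and again for those with incomplete control.

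**The concern.** A failure at the week 4 or week 8 visit meets the primary outcome criteria, so 2.e stops drug. The same failure is absent from the list that governs stopping. If every failure stopped drug, the week 8 qualifier in that list would have no purpose. Two clinicians could therefore treat the same patient differently, each with a section to cite.

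In an open-label study of at most 5 patients, one such decision affects at least a fifth of the data. It determines:

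- how long the patient is exposed to tofacitinib;
- whether later safety findings, and any later acuity, macular oedema or pressure readings, reflect tofacitinib or another agent;
- whether a later case of shingles counts toward the stopping example in G2, which counts cases on tofacitinib;
- whether the patient meets the G3 analysis trigger. That trigger needs six months of therapy, or discontinuation through withdrawal or a cessation indication. A patient stopped early under 2.e, for a reason 2.i does not list, literally fits none of these.

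**Working it through.** The plan gives no figure of its own to reproduce; G3 and G4 make the analysis descriptive. The check is a comparison of the sections, followed by arithmetic on the visit schedule.

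**1. The rules side by side**

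| Section | Failure at or before week 8 | Failure after week 8 |
|---|---|---|
| 2.e | stop and switch | stop and switch |
| 2.i, part i | not listed as a reason to stop | stop |
| 2.i, part ii | silent on whether drug stops; switch once it has | switch |

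The sections agree on late failures and disagree only on early ones. Part ii cannot settle this, because it takes effect only once drug has been stopped.

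**2. Can an early failure stay on drug to week 24?** Take a patient who enters at 2+ cells (section 2.a) and is 1+ at week 4. Grade 1+ exceeds 0.5+, so the early criterion is met. If the eye stays at 1+, with no new lesion or acuity loss, there is no 2-step increase, and the failure entry in 2.i never applies. So the case is possible, but only by the cell or haze route and only without a safety stop.

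**3. Difference in drug exposure.** Nominal visits are weeks 4, 8, 12, 16 and 24 (F2). Difference = week drug ends under 2.i minus week of failure; share = difference / 24.

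| Failure at | Drug under 2.i ends at | Difference | Share of 24 weeks |
|---|---|---|---|
| week 4 | week 24 | 24 − 4 = 20 | 83% |
| week 8 | week 24 | 24 − 8 = 16 | 67% |
| week 4 | week 12 | 12 − 4 = 8 | 33% |
| week 8 | week 12 | 12 − 8 = 4 | 17% |

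The first two rows are maxima for the patient in step 2. The last two are for a new lesion or acuity loss that is still present at week 12 and meets the same criterion in the late block. This assumes that acuity loss is judged against baseline, a reference C1 does not state.

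**4. How often might it arise?** G1 allows at most 5 patients, so each is at least 1/5 = 20% of the sample. G3 expects 40–60% to meet the endpoint: 0.4 × 5 = 2 to 0.6 × 5 = 3 failures. The share of failures that are early, *e*, is not in the documents, so I vary it as an assumption. With failure rate *f*, P(at least one early failure) = 1 − (1 − *f·e*)^5.

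| *e* (assumed) | Expected early failures | P(at least one) | Largest exposure difference, patient-weeks of 5 × 24 = 120 |
|---|---|---|---|
| 0% | 0 | 0% | 0 |
| 50% | 1.0–1.5 | 1 − 0.8^5 = 67% to 1 − 0.7^5 = 83% | 20–30 |
| 100% | 2–3 | 1 − 0.6^5 = 92% to 1 − 0.4^5 = 99% | 40–60 |

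The last column takes every early failure at week 4 and 20 weeks for each, so it is an upper bound.

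**5. The boundary.** Visits may move by 2 weeks either way, so the week 8 visit can fall as late as week 10. The plan does not say whether such a visit counts as at week 8 or after it.

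**The case against.** The strongest reply is that these are not two opposite instructions. Section 2.e is a general statement about risk, while 2.i is the dedicated cessation section. The 2.i list contains no word limiting it to its entries and nowhere says that an early failure continues on drug. This stands as far as it goes: continuation is inferred from the qualifier, so the fault is a mismatch of scope. It does not remove the gap, because 2.e is stated without limit and nothing says which section prevails.

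Stronger readings that the documents do not support:

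- *Any early failure costs 83% or 67% of study drug under one rule and none under the other.* Two of the three early criteria recur in the late block, so a persisting lesion or acuity loss can stop drug under 2.i at week 12.
- *The primary result depends on which rule is followed.* If an early failure is final, the count is the same either way.
- *The 3.f ban makes the rules impossible to follow together.* It sits in paragraphs on starting and background therapy and aims to protect the efficacy reading. The switch provisions concern patients already classed as failures, so they can be read as exceptions. What remains is that no exception is written.
- *Many improving patients will be failed at week 4 because response is only beginning.* D2 does say "Treatment with tofacitinib leads to a clinical response starting at 4-8 weeks after initiation of therapy", but it cites rheumatoid and psoriatic arthritis trials. Entry also requires a response to steroids, and Table 2 has patients on 30 mg/day at week 4. The documents give no early failure rate.

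It is also fair that this is a descriptive pilot, that bottle collection and dispensing (F4) already allow drug status to be derived, and that follow-up after stopping is described as being for safety, so later efficacy readings may be few.

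**Conclusion.** The inconsistency is real but narrow. For a failure at or before week 8, 2.e stops tofacitinib, 2.i implies that the failure alone does not, and no section reconciles them. Late failures are unaffected.

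The nominal difference in exposure ranges from 4 to 8 weeks (a lesion or acuity loss that stops drug at week 12) up to 16 to 20 weeks (a cell or haze failure that meets no late criterion or safety stop). The unchanged failure count assumes that an early failure is final, which the plan does not say outright. How many patients would be affected is unknown: from none to an expected 2 to 3 of 5 over the assumed range of early shares.

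No formal inference depends on this. It should still be corrected, because staff need one instruction on whether a participant continues study drug, and because each patient is at least 20% of what will be described.

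**What to change.** Amend the wording as follows:

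- Reconcile 2.e and the 2.i list, together with C1, 2.i part ii and G3, so that one rule states what happens to study drug after a failure at or before week 8 and after a later failure. Which clinical rule applies is for the investigators to decide.
- State how the visit window bears on the week 8 boundary.
- Say in 3.f whether the ban on starting another steroid-sparing agent still applies after failure.
- Word the G3 trigger so that a patient stopped for early failure, if that is the rule chosen, is covered.
- Report each later assessment as on or off tofacitinib, and do not attribute readings made after a switch to tofacitinib.

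The cost is one protocol amendment and a drug-status label, which can be built from the drug accountability records already collected. It needs no extra visits or patients.

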### **ii Monitoring after tofacitinib cessation**

- If a patient is not a treatment failure as defined by the primary outcome measure at the time of tofacitinib cessation, they will be monitored for disease relapse
- If a patient is a treatment failure at the time of tofacitinib cessation, they will be switched to another steroid sparing agent at the discretion of their treating physician
- Patients who discontinue tofacitinib treatment will remain in the study and be followed to obtain safety data.

## **2.j Adjustment of tofacitinib therapy**

### **i Indications for dose reduction of tofacitinib therapy to 5mg daily**

- moderate to severe renal impairment
- ESRD requiring hemodialysis
- moderate hepatic impairment

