### **2.a Exclusion Criteria**

- presence of an active or uncontrolled systemic rheumatologic disorder
- suspected or confirmed ocular infection
- chronic or recurring infections, such as HIV
- renal insufficiency, which would preclude safe administration of tofacitinib

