### **3.b Treatment Regimen**

Tofacitinib will be taken as extended release, 11mg, once daily.

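### The dose-reduction rule names moderate but not severe hepatic impairment, so on a literal reading a patient who is severe at entry stays on 11 mg daily

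*Combined protocol and SAP*

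**What the plan says.** Section 2.j (Adjustment of tofacitinib therapy) gives three reasons to reduce the dose to 5 mg a day. Two are renal: "moderate to severe renal impairment" and end-stage disease on dialysis. The third is hepatic, at a single grade: "moderate hepatic impairment". The general regimen is in section 3.b: "Tofacitinib will be taken as extended release, 11mg, once daily". Section D2 gives the alternative approved schedule: "Administration of tofacitinib is approved for 5mg twice daily or 11mg extended release for rheumatoid arthritis".

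The exclusion list in section E2 has four items: active systemic rheumatologic disease, ocular infection, chronic infection, and renal insufficiency that makes the drug unsafe. None concerns liver function. The nearest is "chronic or recurring infections, such as HIV", supported by section 2.e: "Standard laboratory screening is performed in all patients to assess for latent / chronic infection, such as TB".

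Section 2.i has two stopping rules that could reach a liver problem: "New elevation of ALT or AST > 3x upper limit of normal" and "Any patient hospitalized secondary to treatment with tofacitinib as determined by a rheumatology research clinician". Table 1 schedules a metabolic panel and hepatitis B and C serology at week 0, without a liver threshold or an action on the result.

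**The concern.** A dose rule for organ impairment should not become more permissive as impairment worsens. Here the kidney is covered at every grade from moderate upward, while the liver is covered at moderate only. Unless another rule catches the severe case, the written plan leaves that patient on the default dose, above the dose chosen for someone less impaired. What is at stake is the safety of an individual participant. The descriptive analysis, the treatment-failure endpoint and any efficacy conclusion are unaffected.

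**Working it through.** The plan states no figure to reproduce. The check is a rule-by-rule trace, followed by a dose ratio.

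**Kidney and liver side by side**

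| Rule | Kidney | Liver |
|---|---|---|
| Exclusion at entry (E2) | Insufficiency that makes the drug unsafe | None; chronic infection may cover viral hepatitis |
| Stopping (2.i) | New renal failure that makes the drug unsafe | New ALT/AST rise above 3 times the upper limit |
| Reduction to 5 mg (2.j) | Moderate, severe, and dialysis | Moderate only |

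**Trace for one patient.** Take severe hepatic impairment present at entry, not due to chronic infection, with no other organ problem, no new enzyme rise and no hospitalization attributed to the drug.

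1. Inclusion and exclusion criteria: no hepatic requirement and no hepatic exclusion, so the patient is eligible.
2. Section 2.i: the enzyme rule requires a new rise. It measures a change in enzymes, not a grade of impairment, so it does not fire. The hospitalization rule does not fire.
3. Section 2.j: the hepatic line names moderate only, so it does not fire on its wording.
4. Section 3.b then applies: 11 mg once daily.

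By hepatic status at entry, the literal result is: none or mild, 11 mg; moderate, 5 mg; severe, 11 mg.

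**Dose ratio.** Inputs are 5 mg daily (2.j), 11 mg extended release (3.b), and 5 mg twice daily as the alternative approved regimen (D2).

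- Using the alternative regimen: 2 × 5 = 10 mg a day; 10 / 5 = 2.0.
- By nominal milligrams: 11 / 5 = 2.2.

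**Longest duration.** The study lasts 24 weeks, or 24 + 2 = 26 with the visit window. For a responder entering the 1-year extension it is 24 + 52 = 76 weeks, or 26 + 52 = 78 with the window. The extension figures assume that the same dose continues, because the documents give no separate extension dose. They are upper bounds and require the impairment to go unaddressed throughout.

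The documents do not say how common severe hepatic impairment is among candidates, so no probability of meeting the gap is calculated.

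**The case against.** The strongest reply is that silence is not a dose assignment. Section 2.j lists indications for reduction without claiming to be exhaustive, and nowhere does the plan prescribe 11 mg for severe hepatic impairment. That result comes only from combining the omission with the general regimen line. A specialist required to reduce the dose for moderate impairment would hardly give the full dose to someone worse, and might not enrol that patient. Baseline chemistry, laboratory review at visits (5.e) and weekly safety meetings (I1) also stand in the way. All of this is fair, and it is why the point is small. It does not remove the gap, because none of these is a dosing rule. Nor can the bare word *moderate* safely be read as moderate or worse, since the same short list spells out the severe grade for the kidney.

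A reader might infer three stronger conclusions that the documents do not support:

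- **That severe hepatic impairment must be excluded or the drug stopped.** The only internal comparator is renal, and 2.j allows 5 mg daily for severe renal impairment and even on dialysis. Section D3 says the approved rheumatoid arthritis dose is used, and section F3 has the package insert handed out, but the insert's hepatic content is not in the documents. It neither closes the gap nor justifies a mandatory exclusion.
- **That impairment developing on study also ends at 11 mg.** A gradually worsening patient meets the moderate trigger first, and no rule restores the higher dose. An injury with a new enzyme rise above the threshold is stopped under 2.i. The gap is shown only for impairment already present at entry.
- **That a doubled dose means a known excess of harm.** The documents link the ratio to no exposure or toxicity figure.

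**Conclusion.** The concern holds in limited form. No exclusion, reduction or stopping rule names severe hepatic impairment. On a literal reading, a patient with non-viral severe impairment at entry defaults to about twice the daily dose set for moderate impairment (2.0 to 2.2 times).

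This rests on three assumptions: that 2.j is read as written, that section 3.b governs whatever 2.j does not mention, and that the chronic-infection exclusion removes viral causes. The partial safeguards narrow the gap without closing it. With at most 5 patients and specialist management it will probably not be met, and it changes nothing in the endpoint, the analysis or the interpretation of this descriptive pilot. It is a minor safety correction, worth making because the remedy is so cheap.

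**What to change.** **Main change.** In section 2.j, extend the hepatic line to read *moderate to severe*, matching the renal line. Severe impairment can then never carry a higher dose than moderate. The cost is two words, with no added visit, test or loss of eligibility. The change needs no boundary between moderate and severe, because both receive 5 mg. The protocol does not define *moderate*, so the lower boundary remains a clinical judgement, as it is now.

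**Stricter alternative, at the sponsor's choice.** Add severe hepatic impairment to the exclusion criteria, parallel to the renal exclusion. This costs one line and slightly narrower eligibility. The sponsor would also have to state how severe is graded and confirm that the baseline assessments are enough to grade it.

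Neither change shortens the interval between scheduled metabolic panels (weeks 0, 4, 12 and 24, so at most 24 − 12 = 12 weeks apart by nominal dates). Neither would therefore detect impairment arising on study any sooner.

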## **E3 Study Drug**

### **3.a Description**

Tofacitinib is a small molecule that inhibits Janus kinase (JAK). Specifically, it inhibits JAK1 and JAK3 and to a lesser extent JAK2. This inhibition occurs downstream of multiple pro-inflammatory cytokines, such as IL-2, IL-6, & IFN, and explains the anti-

---

inflammatory effects of tofacitinib. It has demonstrated clinical efficacy in multiple inflammatory disorders: rheumatoid arthritis, psoriatic arthritis, and ulcerative colitis.

